occlusion in a rat model); they measured soluble ST2 mRNA in lung, kidney, and liver tissue samples obtained at prespecified time-points. The liver and kidneys did not participate in ST2 production during any of the studied periods. Concentrations of sST2 have been implicated in the presence and severity of heart failure with particular value for prognostication. It was reviewed the use of sST2 as a prognostic biomarker in heart failure, including present and future directions in this exciting area (*Bhardwaj and James 2010*)

Much published work has examined and confirmed the beneficial physiological effects of aerobic physical activity or moderate intensity (55%–70% of maximal heart rate (MHR), rate of perceived effort (RPE) of 11–13 on the Borg scale) continuous training, known as MICT. World Health Organization (WHO) recommends a minimum of 150 min per week of aerobic physical activity at moderate continuous intensity to maintain or achieve health *(Wood et al., 2019).*

Exercise of high submaximal intensity performed in intervals of 1 to 4 minutes, also called high-intensity interval training (HIIT), has been tested in a multiple studies on patients with heart failure with reduced ejection fraction, showing that HIIT was superior to moderate continuous training (MCT) in improving exercise capacity, quality of life, endothelial function, and left ventricular diameter and ejection fraction. The results were better than those observed in previous studies and meta-analyses of patients with chronic heart failure. They also prompted discussions of whether HIIT should be included in standard care of patients with chronic heart failure. *Guidelines for rehabilitation in patients with cardiovascular disease (JCS 2014).*

Despite concerns regarding patient adherence, several studies have shown irrefutable advantages of HIT in patients with cardiac failure. It is interesting that HIT protocols, the total exercise volume, and time commitment have been significantly lower compared to moderate-intensity training, and yet its use still shows various positive physiological benefits that are at least comparable with moderate-intensity protocols. It is also important to note that HIT has been shown to be safe, tolerable, and enjoyable for patients with cardiovascular disease, eliminating any major concerns of an increase in adverse effect risk (*Hussain et al., 2016*).

CHAPTER III PATIENTS AND METHODS

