The current study is designed to compare the effect of high intensity interval training versus moderate continuous training exercise on soluble ST2 biomarker level in chronic heart failure patients with New York heart association (NYHA) classification I, II.

Patients:

This study will be carried out on sixty male patients suffering from chronic Heart failure NYHA classification (I & II) with an age range from 50 to 60 years old. The patients will be selected from Aldmerdash hospital, Ain shams university and patients will be randomly assigned into two groups. The purpose, nature and potential risk of the study will be explained to all patients.

Ethical considerations:

- Approval of faculty ethical committee.
- The study procedures will be explained for all participants.
- Confidentiality will be assured.
- An informed consent will be taken from each subject prior to participation (Appendix I).

Criteria for the patient selection:

Inclusion Criteria:

The patient selection will be according to the following criteria:

- They will have chronic heart failure (New York heart association class I& II) systolic left ventricular dysfunction.
- Their left ventricular ejection fraction (LVEF) <40%.
- Medical treatment will be optimized at least three months prior to study entry.
- All patients didn't participate in any rehabilitation programs prior to the study.

Exclusion criteria:

Patients who will meet one of the following criteria are to be excluded from the study:

Signs of acute heart failure, unstable angina or severe • arrhythmia three months prior to enrolment in the study.

Pacemakers. •

Chronic obstructive pulmonary disease.

Other disorders counteracting exercise testing conditions • that limit lower limb mobility (for example, burns, fractures)

Pre-existing neuromuscular diseases (for example • Myasthenia Gravis).

Patients will be assigned into two groups with a group A receiving HIIT and group B receiving MICT, both groups will receive their optimal medical treatment.

All patients will be thoroughly evaluated before and • after treatment protocol application.

All patients will receive their prescribed medical • treatment.

Evaluation

Primary outcome to be measured is soluble ST2 biomarker level **Secondary out come** to be measured is ejection fraction, quality of life and peak exercise response.

Soluble ST2 biomarker

.1

The Presage(®) ST2 Assay

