(Critical Diagnostics, CA, USA) is an in vitro diagnostic device that quantitatively measures soluble suppression of tumorigenicity 2 (sST2) in serum and plasma by ELISA (Mueller and Dieplinger 2013).

Procedure: sample will be taken at the cubited vein at the beginning of the program and also at its end.

Echocardiogram.

Left ventricular systolic dysfunction will be assessed using the ejection fraction by 2D simpson method (the percentage of the end diastolic volume ejected during systole).

.2

Resting echocardiographic images will be acquired in accordance with American Society of Echocardiography guidelines by a cardiac sonographer, blinded to group allocation *(Lang et al., 2015).*

Procedure: A commercially available ultrasound system (Vivid S5 or E90, GE Medical Systems, Horten, Norway) equipped with a 2.5-MHz multifrequency phased array transducer will be used to determine the echocardiogram variables by the physician.

3. Minnesota Living with Heart Failure Questionnaire

The questionnaire has 21 items. Assessing the impact of frequent physical symptoms of heart failure. Other items ask about the effects of heart failure on physical and social functions as well as mental and emotional functions. Since treatments might have direct effects on a patient's life in addition to their effects on symptoms and functional limitations of heart failure, questions about side effects of medications, hospital stays and costs of care were included to help measure the overall impact of treatments for heart failure on patients' quality of life.

Procedures: When administering the Minnesota Living with Heart Failure Questionnaire to a subject, the instrument must be

completed fully and it is crucial to explain to the patient why it is important to collect his opinions in order to reduce the number of missing data and therefore maximize the quality of the 10 data collected (Appendix II).

4- Modified Bruce exercise test

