A symptom-limited graded treadmill exercise test (GXT) will be carried out prior to the exercise rehabilitation program to tailor the exercise training program using modified Bruce protocol .The following exercise parameters will be assessed: a) Exercise duration, b) estimated achieved metabolic equivalent of task (METs), c) basal heart rate (BHR), d) peak heart rate (PHR) and peak exercise response. The exercise test will be repeated after completion of the 3-month CR program to assess the change in functional capacity of the patients with respect to the fore-mentioned parameters (*Pescatello et al., 2014*).

Procedure:

Exercise will be performed on a treadmill. The leads of the ECG are placed on the chest wall. The treadmill is started at 2.74 km/hr (1.7mph) and at inclinator gradient of 10% after 3 min incline af the treadmill is increased by 2% and the speed increases. The test should be stopped when the subject cannot continue due to fatigue or pain or due to any other medical condition (*Badawy and Muaidi 2019*).

Training

Management procedures

Group A

Patients will receive medical treatment and will be submitted to the cardiac rehabilitation unit receiving HIIT *(pelliccia et al., 2021).*

Frequency: HIIT, MCT will be in 2 supervised sessions per • week for 12 weeks on treadmill.

Intensity: HIIT included 4 minute intervals aiming 60-85% of • heart rate reserve separated by 3 min active recovery period of moderate intensity exercise 40-59% of heart rate reserve.

Duration: The session lasts 30-40 min included warming up • and cooling down at moderate intensity.

Group B

Patient will receive medical treatment and will be submitted to the cardiac rehabilitation program receiving MICT (Mueller et al., 2021).

Frequency: Moderate continuous training is scheduled 2 times • per week for 12 weeks.

Intensity: exercise will be applied on treadmill (40%-59% of • heart rate reserve)

Duration: 30-40 minutes per session.

Safety: all the procedures will be applied inside the cardiac rehabilitation unit.

Only the patients who will complete the 3 month CR program attending $>\!80\%$ of the exercise training sessions will be included in this study.

Data analysis:

The collected data will be statistically analyzed using descriptive statistics (the mean and standard deviation).

The paired t test will be used to determine the significance level • between pre and post physical therapy treatment.

The level of significance < (0.05).

References

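### Patients are randomised, but only completers with more than 80% attendance are kept, so the groups analysed are not the groups randomised

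*Protocol*

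**What the plan says.** Chapter III, Patients, says of the sixty men that "patients will be randomly assigned into two groups". The text after the exclusion criteria adds: "All patients will be thoroughly evaluated before and" after treatment.

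The last paragraph of the Training section, just before Data analysis, narrows this: "Only the patients who will complete the 3 month CR program attending" more than 80% "of the exercise training sessions will be included in this study". Neither condition appears among the inclusion and exclusion criteria, and neither could, because both are known only once training is over.

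Two statements govern end-of-study data. The sST2 sample is taken "at the beginning of the program and also at its end" (Soluble ST2 biomarker, Procedure). For the treadmill test, "The exercise test will be repeated after completion of the 3-month CR program" (Modified Bruce exercise test). Neither says what happens to a patient who stops early.

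On adherence, Basic Assumptions takes it that every patient will keep to the programme. The last paragraph of Chapter II is mixed: "Despite concerns regarding patient adherence, several studies have shown irrefutable advantages of HIT", but also "HIT has been shown to be safe, tolerable, and enjoyable".

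**The concern.** Randomisation makes the two groups comparable at the start. A filter applied afterwards, on behaviour that the allocated treatment can influence, may undo that. The arms differ in intensity (60-85% v 40-59% of heart rate reserve in the work phase), so the reasons for stopping or missing sessions may differ between them. In heart failure, a patient who stops because he is getting worse could plausibly also have a worse sST2, ejection fraction, quality-of-life score or exercise result. Dropping such patients flatters the arm that loses more of them.

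The hypothesis compares HIIT with MICT, so the retained groups are the ones from which that conclusion would be drawn. The paired pre/post t test, the only test named under Data analysis, is also exposed: if patients who do badly are removed, the remaining patients in that arm appear to improve even when training does nothing.

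**Working it through.** **Passages side by side.** Patients: all sixty randomised. After the exclusion criteria: all evaluated before and after. End of Training: only completers with more than 80% attendance belong to the study. These agree only if nobody stops and nobody misses more than four sessions, which is what Basic Assumptions supposes. An attendance rule has work to do only if some patients fall short.

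**Attendance threshold.** Both arms train twice a week for 12 weeks: 2 × 12 = 24 sessions. 0.80 × 24 = 19.2. Attending 19 gives 19/24 = 79.2%, which fails; 20 gives 20/24 = 83.3%, which passes. Five missed sessions exclude a patient.

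**Size.** There is no figure of the plan's own to reproduce: the protocol gives no loss rate, SD, effect size or power. Everything below is an illustration. Assumptions: 1:1 allocation (30 per arm), no true effect, and a latent attendance score L ~ N(0,1). Change in SD units is D = ρL + √(1−ρ²)e, and a patient is excluded if L falls below the p-quantile z_p. The expected shift in mean change among those retained is

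shift = ρ · φ(z_p)/(1−p),

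and the between-arm bias is the difference of the two shifts. The factor φ(z_p)/(1−p) is:

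- p = 30%: 0.3477/0.70 = 0.497
- p = 10%: 0.1755/0.90 = 0.195
- p = 3.3% (1 of 30): 0.0742/0.967 = 0.077

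For 30% v 10%, 0.497 − 0.195 = 0.302. Multiplying by ρ = 0.3, 0.5 and 0.8 gives 0.09, 0.15 and 0.24 SD. False-positive rates come from simulation (200,000 runs per case, two-sided 0.05).

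| Excluded | Test | Bias or shift (SD), ρ = 0.3 / 0.5 / 0.8 | False-positive rate |
|---|---|---|---|
| 30% v 10% | between arms | 0.09 / 0.15 / 0.24 | 6.0 / 8.1 / 15.0% |
| 10% v 3.3% | between arms | 0.04 / 0.06 / 0.09 | 5.2 / 5.5 / 6.6% |
| 30% v 30%, same ρ in both arms | between arms | 0 | 5% |
| 30% | paired, one arm | 0.15 / 0.25 / 0.40 | 10 / 21 / 55% |
| 10% | paired, one arm | 0.06 / 0.10 / 0.16 | 6 / 8 / 13% |
| 3.3% | paired, one arm | 0.02 / 0.04 / 0.06 | 5 / 5 / 6% |

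The between-arm test is the one the hypothesis calls for, though Data analysis does not name it. With ρ = 0 there is no bias and the rate is 5%. The sign reverses if the other arm loses more, or if those excluded had the better change.

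Equal losses are not safe in themselves. The zero for 30% v 30% needs the same link between attendance and outcome in both arms. With ρ = 0.5 in one arm and 0 in the other, the bias is 0.5 × 0.497 = 0.25 SD.

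**Cross-check with a cruder model.** Let a share q of an arm be excluded and let those patients do g SD worse than the rest; the retained mean then shifts by q·g. With q = 0.30 v 0.10 and g = 0.5 to 1.0, the bias is (0.30 − 0.10) × g = 0.10 to 0.20 SD and the false-positive rate 6.4% to 10.6%, the same order as above.

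**The case against.** The strongest reply is that harm is possible rather than shown. The protocol contains no loss rate and no evidence that the arms will lose different patients. Both arms have the same frequency, session length, treadmill and setting. The remark about adherence to high-intensity training is general commentary, and the same paragraph calls such training tolerable. The largest figures above need 30% of an arm excluded and a correlation of 0.8; at 10% v 3.3% the between-arm test is close to nominal. All of that stands. The numbers show what could happen and are not a forecast, so the case for change rests on the principle of analysing as randomised.

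An unseen SAP might define an analysis of everyone randomised. That helps little: the protocol itself fixes who belongs to the study, so such an SAP would contradict it, and no SAP can recover end values that were never collected.

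It is also fair that the end of the programme could mean the calendar end, with all patients sampled then. The end-measurement wording therefore needs clarifying, but it is not an error in its own right. Finally, analysing everyone cannot be done literally where 12-week values remain missing; that limits the remedy but does not justify the exclusion.

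**Conclusion.** The concern holds. The protocol randomises sixty patients and then admits to the study only those who meet two conditions observed after randomisation, with no analysis of all randomised patients beside it. That much follows from the text alone.

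The size of the effect cannot be fixed from the document. It is nil if exclusion is unrelated to outcome and small if losses are few. Under the assumed 30% v 10% exclusion the between-arm false-positive rate is 6% to 15%. For the paired test with 30% excluded it is 10% to 55%, and equal losses in the other arm give that test no protection. The sponsor cannot know the pattern of loss in advance, and uncollected end values cannot be retrieved later, so the rule should be changed.

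**What to change.** Replace the attendance sentence at the end of the Training section with wording such as:

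> All randomised patients are analysed in the group to which they were assigned, regardless of attendance. The end-of-programme blood sample, echocardiogram, questionnaire and exercise test are sought at 12 weeks from every randomised patient, including those who stop training. An analysis restricted to patients attending more than 80% of sessions is secondary (per-protocol).

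Report by arm how many stopped or fell below the threshold, and why. The word *sought* is deliberate: whether a particular patient can undergo a given assessment remains a clinical decision that this wording does not touch. How remaining missing values are handled should be stated with the analysis.

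The cost is protocol wording plus 12-week visits for patients who stop. The estimated effect will be somewhat diluted by non-adherence, and bias remains where values stay missing. In the 30% v 10% illustration, obtaining every end value brings the bias to 0. If half of the non-attenders' values are obtained at random (a favourable assumption), the factors become (0.3477/2)/0.85 = 0.205 and (0.1755/2)/0.95 = 0.092. The difference, about 0.112, leaves 0.03 / 0.06 / 0.09 SD for ρ = 0.3 / 0.5 / 0.8, with false-positive rates of 5.2 / 5.5 / 6.4%.

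### The only test named for sST2 is a within-arm paired t test; it neither compares HIIT with MICT nor uses the baseline value as a covariate, and the analysis scale is not fixed

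*Protocol*

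**What the plan says.** In Chapter III, the Evaluation section states: "Primary outcome to be measured is soluble ST2 biomarker level". The assay "quantitatively measures soluble suppression of tumorigenicity 2 (sST2) in serum and plasma by ELISA", and blood is drawn "at the beginning of the program and also at its end". Every analysed patient therefore has a baseline and a final value on a continuous scale.

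The Patients section says "This study will be carried out on sixty male patients" and "patients will be randomly assigned into two groups". It gives no allocation ratio. The Hypothesis section, placed before Chapter II, predicts a difference between the two training methods on sST2.

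The Data analysis section has three elements, applied to all collected data: "descriptive statistics (the mean and standard deviation"), then "The paired t test will be used to determine the significance level" between the pre and post measurements, then "The level of significance < (0.05"). It names no test between arms, no use of the baseline value as a covariate and no measurement scale.

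**The concern.** The named test answers a different question from the one posed. A paired t test asks whether sST2 changed within an arm. Two such tests, one per arm, do not estimate the HIIT-MICT difference or give it a confidence interval, even if one is significant and the other is not.

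If the gap is filled in the most obvious way, by a t test on change scores between arms, precision is lost because the baseline value is not used to best effect. With 60 patients and no stated sample-size derivation, there is little to spare.

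Scale is a further question. sST2 is a concentration and cannot be negative. If its distribution has a long upper tail, a few high values will dominate raw means and SDs. If the scale is chosen only after the data are seen, the choice is open to the charge of being data-driven.

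**Working it through.** **Inputs.** From the protocol: 60 patients, two randomised arms, sST2 at start and end, significance level 0.05. Assumed, because the protocol does not give them: 30 per arm, a two-sided test, and the pre-post correlation, spread, distribution and effect size of sST2. The protocol has no power or sample-size figure to reproduce.

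**Step 1: does the named test match the hypothesis?** The hypothesis concerns the difference between arms, (end A) − (end B) given comparable baselines. The paired t test estimates (end − start) within A, or within B. No stated step links the two.

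**Step 2: value of baseline adjustment.** Let the pre and post variances both be σ² and their correlation rho.

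- Change score: variance = 2σ²(1 − rho)
- Adjusted for baseline: residual variance = σ²(1 − rho²)
- Ratio = 2(1 − rho) / [(1 − rho)(1 + rho)] = 2/(1 + rho)

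| Assumed rho | Variance ratio | CI width ratio (square root) | Patients with adjustment that match 60 on change scores, 60(1 + rho)/2 |
|---|---|---|---|
| 0.5 | 1.33 | 1.15 | 45 |
| 0.7 | 1.18 | 1.08 | 51 |
| 0.85 | 1.08 | 1.04 | 55.5 |

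The ratio depends on the first two moments only, so it needs no assumption about skewness. It ignores the one degree of freedom spent on the slope and chance baseline imbalance, both small here.

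**Step 3: power with and without adjustment, raw scale.** Simulation: 30 per arm, log-normal sST2, log-scale correlation 0.7, sST2 20% lower in one arm, two-sided 0.05.

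- Log-SD 0.4: raw change test 67%, raw adjusted model 79%
- Log-SD 0.5: raw change test 47%, raw adjusted model 59%

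The gap is wider than 1.18 alone implies. A proportional reduction shrinks the post-treatment variance in one arm, and the raw-scale correlation is slightly below 0.7.

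**Step 4: what the log scale adds on top of adjustment.** Same settings, both models baseline-adjusted:

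| Assumed distribution | Raw scale | Log scale | Difference (points) |
|---|---|---|---|
| Log-normal, log-SD 0.3 | 96.4% | 97.2% | +0.8 |
| Log-normal, log-SD 0.4 | 79.3% | 83.8% | +4.5 |
| Log-normal, log-SD 0.5 | 58.5% | 65.9% | +7.4 |
| Log-normal, log-SD 0.6 | 40.6% | 49.7% | +9.1 |
| Normal, CV 0.3, 20% reduction | 94% | 89% | −5 |

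In the normal case an unadjusted raw change test has 90%, so logging would give back the whole gain from adjustment.

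**Step 5: validity.** With no effect, the raw-scale tests reject in 4.1% to 5.0% of trials (log-normal, CV 0.3 to 1.0). Raw-scale testing does not inflate type I error.

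**The case against.** The strongest reply is that the protocol never says the analysis is on the raw scale. A paired t test on log values is still a paired t test, and transformation is a detail commonly left to an SAP, which is not shown here. That stands. The missing scale is a reason to pre-specify it, not an error in itself.

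A reader might infer that, because sST2 is a positive ELISA concentration, it must be right-skewed, and that a mean-and-SD analysis therefore loses precision for certain. The documents do not support this. They give no SD, CV or distribution for sST2. The eligibility criteria (men aged 50 to 60, NYHA I-II, LVEF below 40%, optimised treatment, no recent acute heart failure) may narrow the spread. A log-normal simulation with a proportional effect builds in the model under which logs do best. With normal data the sign reverses.

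The reply does not reach the main point. The test that the protocol does state is within-arm and the hypothesis is between-arm. Leaving the scale to an SAP does not change that, and the benefit of baseline adjustment does not depend on skewness.

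**Conclusion.** The point holds in a limited form. The stated primary analysis does not compare the arms and does not use the baseline sST2 value as a covariate. Relative to an unadjusted change-score comparison, adjustment removes a variance excess of 8% to 33% for correlations from 0.85 down to 0.5, given equal pre and post variances. In the two simulated settings it was worth about 12 points of power.

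The scale is a secondary and conditional matter. The log scale gains about 1 to 9 points over raw-scale adjustment for log-SDs of 0.3 to 0.6, and loses about 5 if sST2 is near-normal. All correlations, spreads and effects are assumptions.

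Nothing here shows that raw-scale t tests would give false positive results. Once the arms are compared, the choice of adjustment and scale is one of efficiency.

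**What to change.** In Data analysis, name as primary a linear model of end-of-programme sST2 on arm and baseline sST2, and report the adjusted HIIT-MICT difference with its 95% CI. Keep the paired t tests as descriptive within-arm results.

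State the scale before any sST2 data are seen. If right skew is expected, model log(sST2) with log(baseline), report the between-arm ratio of geometric means with 95% CI, and describe sST2 by geometric mean or median and quartiles alongside the mean and SD. Keep the other scale as a sensitivity analysis.

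The cost is a few lines of text. No extra samples or patients are needed. The small downside is that a log-scale result is read as a ratio instead of a difference.

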Aerobic exercises can be continuous, of moderate intensity or intercalating high and low-intensity efforts. High-intensity interval training (HIIT) is currently one of the most effective methods for improving cardiorespiratory and metabolic function. HIIT involves repeated activities, from short to long ones, of high-intensity exercises combined with periods of active or passive recovery (*Tschakert and Hofmann 2013*).

Moderate-intensity continuous training (MICT) is regarded as a successful approach to CR because of its efficacy and safety. Some studies found that MICT can reduce cardiovascular risk and cardiovascular mortality. MICT entails longer durations of moderate-intensity continuous aerobic activity, maintaining intensity between 60 and 80% (VO2peak or reserve heart rate) (Yue et al.,2022).

Recently reported that HIIT is superior to traditional continuous aerobic training in improving cardiac autonomic function and suggested that the effect verified on post-HIIT autonomic

function was related to improve bar reflex modulation and vagal control (*Kiviniemi et al. 2014*).

Several studies reported exercise-induced Moderate Intensity Continuous Training (MICT) favorable cardiac chambers remodeling in post-infarction and in heart failure (either with reduced or preserved ejection fraction) patients (Mueller et al., 2021).

Statement of the Problem:

Is there a significant difference between high intensity interval training versus moderate intensity continuous training on soluble ST2 biomarkers in chronic heart failure?

The Purpose of the Study:

To determine the effect of high intensity interval training versus moderate intensity continuous training on soluble ST2 biomarkers in chronic heart failure.

Significance of the Study:

A recent study of incident HF conducted between 1998 and 2017 in the United Kingdom (UK), age-adjusted rates of first hospitalizations increased by 28% for both all-cause and HF admissions, and by 42% for non-CV admissions. The risk of HF hospitalization is 1.5 times higher in patients with diabetes compared to controls. AF, a higher body mass index (BMI), and higher glycated haemoglobin (HbA1c), as well as a low estimated glomerular filtration rate (eGFR) are strong predictors of HF hospitalizations (Lawson et al., 2019).

Biomarkers have made a significant contribution to the diagnosis and prognosis of disease. Although strongly associated with

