Patients who will meet one of the following criteria are to obe excluded from the study:

Signs of acute heart failure, unstable angina or severe .1 arrhythmia three months prior to enrolment in the study.

Pacemakers. .2

.3

Chronic obstructive pulmonary disease.

Other disorders counteracting exercise testing conditions .4 that limit lower limb mobility (for example, burns, fractures)

Pre-existing neuromuscular diseases (for example .5 neuromuscular disorder).

Basic Assumptions:

It will be assumed that:

- 1. The primary medical assessment will be done to every participating patient which includes:
- -Complete medical history (personal, present and past)
- Referral from the physician.
- -homodynamic stability without need for vasoactive drugs.
- 2. All patients will stick to the program and will follow instructions.
- 3. All other factors which may influence the outcome such as noise and distraction will be controlled.

Hypothesis:

It will be hypothesized that there will be a significant difference between high intensity interval training and moderate intensity continuous training on soluble ST2 biomarker in patients with chronic heart failure.

CHAPTER II

LITRATURE REVIEW

Heart Failure (HF) is a clinical syndrome characterized of typical symptoms breathlessness, ankle swelling and fatigue that may be accompanied by signs (e.g. elevated jugular venous pressure, pulmonary crackles and peripheral edema) caused by a structural and/or functional cardiac abnormality, resulting in a reduced cardiac output and/ or elevated intracardiac pressures at rest or exertion (*Ponikowski et al., 2016*).

Heart failure is a syndrome characterized initially by left ventricular dysfunction that triggers countermeasures aimed to restore cardiac output. These responses are compensatory at first but eventually become part of the disease process itself leading to further worsening cardiac function (Yancy et al., 2016).

The American College of Cardiology and The American Heart Association ACC/AHA defines Systolic Heart Failure (SHF) as a complex clinical syndrome resulting from any structural or functional cardiac abnormality that impairs the ability of the ventricle to eject blood with manifestations of dyspnea, fatigue, exercise intolerance and fluid retention leading to splanchnic congestion and/or peripheral edema (Yancy et al., 2013).

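### The only test named is a paired pre-post t test, so the HIIT-versus-MICT hypothesis on sST2 has no matching analysis

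*Protocol*

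**What the plan says.** The question is comparative everywhere it is posed in the protocol:

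- Statement of the Problem: "Is there a significant difference between high intensity interval training versus moderate intensity continuous training on soluble ST2 biomarkers".
- Hypothesis: "there will be a significant difference between high intensity interval training and moderate intensity continuous training on soluble ST2 biomarker".
- Opening of Chapter III: "The current study is designed to compare the effect of high intensity interval training versus moderate continuous training exercise on soluble ST2 biomarker level".
- Chapter III, Patients: "patients will be randomly assigned into two groups".
- Evaluation: sST2 is the primary outcome, sampled "at the beginning of the program and also at its end".

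Chapter III, Data analysis, has three elements: means and SDs, a 0.05 significance level, and one test. On the test it says "The paired t test will be used to determine the significance level" "between pre and post physical therapy treatment". It does not say whether this is done in each arm or in all patients together. No unpaired t test, ANCOVA, group-by-time term or other between-group test appears anywhere in the protocol text at hand.

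**The concern.** The hypothesis concerns a difference between two randomised arms, while the test concerns a change within patients. Followed exactly, the analysis leaves the trial's only hypothesis untested.

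Two consequences follow. First, a pre-post change in one arm mixes any training effect with the passage of time and regression to the mean, which the randomised comparison is there to remove. Second, with nothing else to go on, an author or reader is likely to compare the two within-arm p values. That comparison does not hold its error rate at 5%, and it hides real differences whenever both arms improve clearly.

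**Working it through.** **No figure to reproduce.** The protocol gives 60 patients but no expected change, SD or power. The mismatch itself needs no arithmetic:

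| Element | Contrast |
|---|---|
| Problem, hypothesis, design | sST2 effect of HIIT minus that of MICT |
| Paired test in each arm | Mean change in HIIT against 0; mean change in MICT against 0 |
| Paired test, pooled | Mean change over all patients against 0; group does not enter |

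Neither form of the paired test contains the first contrast.

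**Size of the consequence, if arms were compared by which paired test is significant.** This rule is inferred and is not in the protocol.

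Inputs:
- 60 patients in two groups (Chapter III, Patients). The ratio is not stated; 30 per arm is assumed.
- Level 0.05 (Data analysis). Sidedness is not stated; two-sided is assumed.
- dz = mean change / SD of change. No value is given, so a range is shown.
- 24 per arm as a second scenario, assuming a 20% loss. Only completers with more than 80% attendance are kept, and no loss figure is given.

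Formulas:
- Power p of a paired t test: noncentral t with n − 1 df and noncentrality dz·√n.
- With the same true change in both arms, P(exactly one significant) = 2p(1 − p).

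| dz (both arms) | p, n = 30 | 2p(1 − p), n = 30 | 2p(1 − p), n = 24 |
|---|---|---|---|
| 0 | 0.050 | 0.095 | 0.095 |
| 0.2 | 0.185 | 0.302 | 0.263 |
| 0.4 | 0.563 | 0.492 | 0.498 |
| 0.5 | 0.754 | 0.371 | 0.455 |
| 0.6 | 0.888 | 0.199 | 0.316 |
| 0.8 | 0.988 | 0.023 | 0.071 |

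Example, dz 0.5 and n = 30: 2 × 0.754 × 0.246 = 0.371. The maximum is 0.50, where p = 0.5 (dz about 0.37 at n = 30). At 30 per arm the rate falls below 0.05 only above dz 0.74. A simulation of 50,000 trials at n = 30 gave 0.095, 0.303, 0.371 and 0.022 at dz 0, 0.2, 0.5 and 0.8. A two-sample t test on the same data rejected in 0.048 to 0.052.

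**The reverse error.** Take true changes of dz 0.8 and 1.6:
- Both paired tests are significant with probability 0.988 at 30 per arm and 0.963 at 24.
- A two-sample t test of change, for a difference of 1.6 − 0.8 = 0.8 SD, has noncentrality 0.8 × √(30/2) = 3.10 and power 0.861 at 30 per arm (0.774 at 24).

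**Pooled reading.** With 60 patients the paired test is significant with probability 0.99998 when both arms change by 0.8 SD, and 0.99996 (simulated) when they change by 0.4 and 1.2 SD. It cannot tell equal arms from very different ones.

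**What a between-group test could detect.** A two-sample t test of change with 30 per arm has 80% power for a difference of about 0.74 SD of change, and 48% power at 0.5 SD. With 24 per arm the 80% figure rises to about 0.83 SD.

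**The case against.** The strongest reply is that a statistical analysis plan may exist and may name a between-group test. The protocol's analysis text is brief, does not call the paired test primary or exclusive, and does not tie it to the hypothesis. A paired test is also a valid way to describe change over the programme. On this view a test has been left out, and nothing is stated wrongly.

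That does not remove the point. The protocol has its own analysis section, refers to no separate plan, and fixes one named test for one named contrast, which is not the contrast it hypothesises. Even if a separate plan added the right test, this section would still conflict with the protocol's own question and would need correcting.

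Three parts of the objection do stand:
- The hypothesis is undecidable only under the analysis as written. The planned data would support the comparison fully.
- The rates of 9.5% to 50% depend on an inferred decision rule, equal allocation, two-sided testing and normally distributed changes. They are illustrations and not this trial's error rate. The 0.8 and 1.6 SD example uses very large effects.
- ANCOVA is one sound remedy. A two-sample test of change or a group-by-time interaction would also close the gap.

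**Conclusion.** The concern holds. The protocol poses a randomised between-group question on its primary outcome and specifies only a within-patient test, so its stated analysis cannot answer its stated hypothesis. This conclusion rests on the text alone and needs no assumption.

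The numerical illustrations show why side-by-side paired tests are no substitute: the chance of a false contrast exceeds 5% for every common change below about 0.74 SD at the assumed 30 per arm. Because the defect touches the sole hypothesis and the primary outcome, it should be corrected before the data are analysed.

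**What to change.** In Chapter III, Data analysis, name a between-group primary analysis. Suggested wording: *End-of-programme sST2 will be compared between the randomised groups by ANCOVA adjusted for baseline sST2, at a two-sided 0.05 level, reporting the HIIT-minus-MICT difference with its 95% confidence interval.* The same model can serve ejection fraction, the Minnesota questionnaire score and the exercise-test measures. If sST2 is to be analysed on a log scale, fix that before the data are seen.

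Keep the paired pre-post changes as within-group description, state that they are reported by arm, and rest no between-arm claim on them.

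The cost is protocol wording only. Baseline and end samples are already planned in both arms, so no extra patients, visits or assays are needed.
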